#### 8.1.2. Secondary endpoints

Secondary endpoints for both study parts (unless otherwise specified) are:

- Incidence and severity of TEAEs and clinical laboratory abnormalities, according to NCI-CTCAE version 5.0 criteria
- Changes in vital signs: systolic/diastolic blood pressure, heart rate (both after at least 5 minutes of supine rest), temperature, and weight; ECG and ECOG-PS
- Incidence of premature treatment discontinuations and treatment modifications due to AEs and laboratory abnormalities (i.e., treatment compliance)
- Tumor response determined according to RECIST v1.1 and/or GCIG criteria (Cohort 4, if applicable):
  - Confirmed (Part A) and unconfirmed (Parts A and B) ORR
  - Disease control rate (DCR), defined as any response, partial or complete (PR or CR) + stable disease (SD)
  - Time-related endpoints as median time to response, median DOR, median PFS, PFS rate at 6, 12 and 18 months, median OS, OS rate at 12 months and 18 months (if data allow)

- PK parameters of Debio 1143 and Debio 1143-MET1 as defined in the available population PK model (36) and, if appropriate, post-hoc estimates of areas under the curve (AUCs),  $C_{max}$ , and  $C_{min}$ ; serum concentration versus time profiles of nivolumab and, if deemed appropriate, relevant nivolumab PK parameters derived from a population PK model. (37)

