**Table 8-1 Sampling days and times for PK on Cycle 1**

Cycle day	Cycle 1																		
	1					3	8				15					17	22		
Time [h]	0*	0.5 	1.5 	4 	8 	0*	0*	1.5	4 	8 	0*	0.5 	1.5 	4 	8 	0*	0*	1.5	4 
Part A																			
Nivolumab PK	X	-	X	-	X	X	X	-	-	-	X	-	X	-	X	X	X	-	-
Debio 1143 PK	X	X	X	X	X	X	X	X	X	X	X	X	X	X	X	X	X	X	X
Nivolumab ADA	X	-	-	-	-	-	-	-	-	-	X	-	-	-	-	-	-	-	-
Part B																			
Nivolumab PK	X	-	X	-	-	-	X	-	-	-	X	-	X	-	-	-	X	-	-
Debio 1143 PK	X	-	X	X	-	-	X	X	-	-	X	-	X	-	-	-	X	X	X
Nivolumab ADA	X	-	-	-	-	-	-	-	-	-	X	-	-	-	-	-	-	-	-

\* To be performed prior to Debio 1143 administration; At the time of the safety laboratory assessment;

 Just before start of nivolumab infusion;

 At the end of nivolumab infusion;

 4 hours after Debio 1143 administration;

 8 hours after Debio 1143 administration.

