**Table 8-2 Sampling days and times for PK (for Cycle 3 exclusively, irrespective of nivolumab schedule switch)**

Cycle day Time [h]	Cycle 3										
	1					3	15				17
	0*	0.5 	1.5 	4 	8 	0*	0*	1.5 	4 	8 	0*
Part A											
Nivolumab PK	X	-	X	-	X	X	X	X #	-	-	X
Debio 1143 PK	X	X	X	X	X	X	X	X	X	X	X
Nivolumab ADA	X	-	-	-	-	-	X	-	-	-	-
Part B											
Nivolumab PK	X	-	X	-	-	-	X	X #	-	-	-
Debio 1143 PK	X	-	X	X	-	-	X	X	-	-	-
Nivolumab ADA	X	-	-	-	-	-	X	-	-	-	-

\* To be performed prior to Debio 1143 administration;

 Just before start of nivolumab infusion;

 At the end of nivolumab infusion for patients receiving 240 mg Nivolumab on Day 1 and Day 15 (q4w) or 1.5 hours after Debio 1143 administration for patients receiving 480 mg nivolumab on Day 1 (q4w);

 4 hours after Debio 1143 administration;

 8 hours after Debio 1143 administration;

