# PK done for patients remaining under 240 mg nivolumab on Day 1 and Day 15 (q4w),

**Table 8-3 Sampling day and times (for Cycle 6 and EOT exclusively, irrespective of nivolumab switch of schedule)**

Cycle	6		EOT 
Cycle day	1		
Time [h]	0*	1.5 	
Part A and B			
Nivolumab PK	X	-	-
Debio 1143 PK	X	X	-
Nivolumab ADA	X	-	X

\* To be performed prior to Debio 1143 administration;

 At the end of nivolumab infusion;

 At the time of the safety laboratory assessment; For patients entering the Extended study period, the last nivolumab ADA will be collected at C13D1 instead of at EOT.

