19.2. PHARMACOKINETIC PARAMETERS

The PK parameters for Debio 1143, Debio 1143-MET1, and nivolumab in Part A and Part B will be calculated by noncompartmental method described below. If deemed appropriate, a population PK approach may be used and will be reported separately.

The actual elapsed time from Debio 1143 dose administration will be used for Debio 1143 and Debio 1143-MET1 analyses, and the actual elapsed time from the start of Nivolumab infusion will be used for Nivolumab analysis.

The PK calculated using available data include:

Debio 1143 and Debio 1143-MET1:		Part A	Part B
C_{max} (ng/mL)	Maximum concentration in plasma obtained directly from the observed concentration versus time data.	Cycle 1 day 1, day 8, day 15 and day 22 Cycle 3 day 1 and day 15 Cycle 6 day 1	Cycle 1 day 1, day 8, day 15 and day 22 Cycle 3 day 1 and day 15 Cycle 6 day 1
C_{max} (µmol/L)	C_{max} (ng/mL) transformed in molar units according to analyte molecular weight*	Cycle 1 day 1, day 8, day 15 and day 22 Cycle 3 day 1 and day 15 Cycle 6 day 1	Cycle 1 day 1, day 8, day 15 and day 22 Cycle 3 day 1 and day 15 Cycle 6 day 1
t_{max} (h)	Time of maximum concentration, obtained directly from the observed concentration versus time data.	Cycle 1 day 1, day 8, day 15 and day 22 Cycle 3 day 1 and day 15 Cycle 6 day 1	Cycle 1 day 1, day 8, day 15 and day 22 Cycle 3 day 1 and day 15 Cycle 6 day 1
$AUC_{(0-4h)}$ (ng·h/mL)	Area under the concentration-time curve in plasma from zero (pre-dose) to the 4-hour post-dose time point.	Cycle 1 day 1, day 8, day 15 and day 22 Cycle 3 day 1 and day 15	Cycle 1 day 1 and day 22 Cycle 3 day 1

Document: T:\sas\Debiopharm\Debio_1143\CZA60507\Biostatistics\Documentation\SAP\SAP Text\V5

Author: [REDACTED] Version Number: 5.0
Version Date: 19APR2022

Template No.: CS_TP_BS016 Revision 5
Effective Date: 01Apr2018

Reference: CS_WI_BS005

Copyright © 2009, 2010, 2012, 2016, 2018 IQVIA. All rights reserved. The contents of this document are confidential and proprietary to IQVIA Holdings Inc. and its subsidiaries. Unauthorized use, disclosure or reproduction is strictly prohibited.

Debio 1143 and Debio 1143-MET1:		Part A	Part B
AUC _(0-4h) (h·µmol/L)	AUC _(0-4h) (ng·h/mL) transformed in molar units according to analyte molecular weight*	Cycle 1 day 1, day 8, day 15 and day 22 Cycle 3 day 1 and day 15	Cycle 1 day 1 and day 22 Cycle 3 day 1

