19.3. EXPLORATORY PHARMACOKINETIC ANALYSES

The correlations between Debio 1143 PK parameters and efficacy/safety parameters will be produced in an exploratory manner. Analyses of correlation between various Debio 1143 PK parameters with clinical response, QTcF and selected lab parameter grades are described below.

Debio 1143 PK parameters vs. Clinical response

Boxplots will be produced where the y-axis displays the value of C_{max} at Cycle 1 Day 1. The x-axis will display each level of confirmed objective response as described in section 17.1.1. Similarly, the box plots will be produced for each level of cBOR as described in section 17.2.1.3. Finally, a scatter plot with a fitted regression line will be produced, with the x-axis presenting the value of C_{max} at Cycle 1 Day1 and the y-axis presenting the best change in tumor size (lowest percentage change from baseline in SOLD).

The analysis described above will be repeated for the following parameters: C_{max} at Cycle 1 Day 8 and C_{trough} at Cycle 1 Day 8.

Debio 1143 PK parameters vs. QTcF

Document: T:\sas\Debiopharm\Debio_1143\CZA60507\Biostatistics\Documentation\SAP\SAP Text\V5	Version Number: 5.0
Author: ██████████	Version Date: 19APR2022
Template No.: CS_TP_BS016 Revision 5	Reference: CS_WI_BS005
Effective Date: 01Apr2018	

A scatter plot with a fitted regression line will be produced, with the y-axis presenting the absolute QTcF value at Cycle 1 Day 1/0.5 – 2 hours post-dose and the x-axis presenting the value of C_{max} at Cycle 1 Day 1. Horizontal dashed lines will be added for each of the markedly abnormal criteria for QTcF as described in section 18.4.1. Similarly, the same regression plot will be produced except for the relative change from baseline in QTcF.

The analysis described above will be repeated for the following:

- C_{max} at Cycle 1 Day 1 vs. QTcF at cycle 1 day 1/4 – 6 hours post-dose
- C_{max} at Cycle 1 Day 1 vs. change from baseline in QTcF at cycle 1 day 1/4 – 6 hours post-dose
- C_{max} at Cycle 1 Day 8 vs. QTcF at cycle 1 day 8/0.5 – 2 hours post-dose
- C_{max} at Cycle 1 Day 8 vs. change from baseline in QTcF at cycle 1 day 8/0.5 – 2 hours post-dose
- C_{max} at Cycle 1 Day 8 vs. QTcF at cycle 1 day 8/4 – 6 hours post-dose
- C_{max} at Cycle 1 Day 8 vs. change from baseline in QTcF at cycle 1 day 8/4 – 6 hours post-dose
- $MR_{C_{max}}$ at Cycle 1 Day 1 vs. QTcF at cycle 1 day 1/0.5 – 2 hours post-dose

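### SAP 19.2 lists Debio 1143 and MET1 Cmax, tmax and MR_Cmax on days with one post-dose sample (Part B C1D8, C1D15, C3D15, C6D1; Part A C6D1), where they are only a nominal 1.5 h level, its time and a ratio at that time

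*SAP*

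**What the plan says.** Protocol 8.1.2 makes PK a secondary endpoint: "PK parameters of Debio 1143 and Debio 1143-MET1 as defined in the available population PK model", with post-hoc AUC, Cmax and Cmin if appropriate. SAP 19.2 calculates the parameters by the noncompartmental method. It defines Cmax as "Maximum concentration in plasma obtained directly from the observed concentration versus time data", defines tmax as the time of that value, and defines MR_Cmax as the molar ratio of MET1 Cmax to parent Cmax. For all three, the day list is the same in Part A and Part B: C1D1, C1D8, C1D15, C1D22, C3D1, C3D15 and C6D1.

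The sampling differs between the parts. Table 8-1 ("Sampling days and times for PK on Cycle 1") and Table 8-2 give Part A a dense schedule and Part B a sparse one. For Cycle 6, Table 8-3 has a single Debio 1143 row for both parts, "Debio 1143 PK X X", meaning pre-dose and 1.5 h.

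SAP 19.3 plots C1D1 Cmax against response, confirmed best overall response and best change in tumour size. It then adds "The analysis described above will be repeated for the following parameters", naming C1D8 Cmax and C1D8 Ctrough. C1D1 and C1D8 Cmax and MR_Cmax are plotted against QTcF, and C1D1 and C1D8 Cmax against the grades of five laboratory parameters.

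**The concern.** A maximum and its time cannot be observed from one post-dose sample. Whatever the patient's absorption, Cmax on such a day is the concentration in that sample (unless the pre-dose level is higher), tmax is the time of that sample, and MR_Cmax is a ratio at one time rather than a ratio of two maxima.

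Two things are at stake. First, a declared secondary PK output would carry parameter names that the data cannot support. A reader comparing Part B days, or Part B with Part A on C1D8, would partly be comparing sampling schemes. Second, C1D8 Cmax enters the exploratory exposure plots, where differences in absorption timing would act as error on the exposure axis.

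**Working it through.** **Inputs.** X marks in the Debio 1143 rows of Protocol Tables 8-1, 8-2 and 8-3, read against their column headers (19, 11 and 2 columns; row lengths match). Day lists from SAP 19.2. Half-life 5.2 to 7.1 h from Protocol 2.3. True tmax is not in the documents; 0.5 to 4 h is assumed.

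**1. The protocol's own figure.** Protocol 8.2.3 states that there are at least two samplings per day on C1D1, C1D8, C1D15, C1D22, C3D1 and C3D15. Part B totals are 3, 2, 2, 3, 3 and 2, so the statement is correct. It counts the pre-dose sample.

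**2. Post-dose samples.**

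| Day | Part A | Part B | Part B times (h) |
|---|---|---|---|
| C1D1 | 4 | 2 | 1.5, 4 |
| C1D8 | 3 | 1 | 1.5 |
| C1D15 | 4 | 1 | 1.5 |
| C1D22 | 2 | 2 | 1.5, 4 |
| C3D1 | 4 | 2 | 1.5, 4 |
| C3D15 | 3 | 1 | 1.5 |
| C6D1 | 1 | 1 | 1.5 |

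One post-dose sample: 4 of 7 days in Part B, 1 of 7 in Part A.

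**3. Comparison within SAP 19.2.** Part B AUC(0-4h) is listed for C1D1, C1D22 and C3D1 only, and Part A AUC(0-4h) for every day except C6D1. These are exactly the days with a 4 h sample. The limit was applied to AUC but not to Cmax, tmax or MR_Cmax.

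**4. What 1.5 h means.** On C1D8 and C1D22 it carries no infusion footnote. On C1D15, on C6D1, and on C3D15 for patients still on 240 mg, it is tied to the end of the nivolumab infusion, with a window of -5 to +30 min (Table 8-5). The timetable starts the infusion at 0.5 h, so the minimum 30 min infusion would end at 0.5 + 0.5 = 1.0 h, and longer infusions later. SAP 19.1 keeps all post-dose samples whatever their timing.

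**5. Size on C1D8 (illustration).** One-compartment oral model with 24 h dosing at steady state (C1D8 is the eighth consecutive dose). ke = ln 2 / half-life; ka solves ln(ka/ke)/(ka - ke) = tmax; C(t) is proportional to exp(-ke·t)/(1 - exp(-24ke)) - exp(-ka·t)/(1 - exp(-24ka)).

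| Assumed tmax (h) | C(1.5)/Cmax, half-life 5.2 h | C(1.5)/Cmax, half-life 7.1 h | Higher of C(1.5), C(4) over Cmax |
|---|---|---|---|
| 0.5 | 0.89 | 0.92 | 0.89, 0.92 |
| 1 | 0.97 | 0.97 | 0.97, 0.97 |
| 1.5 | 1.00 | 1.00 | 1.00, 1.00 |
| 2 | 0.98 | 0.98 | 0.98, 0.98 |
| 3 | 0.86 | 0.89 | 0.96, 0.96 |
| 4 | 0.75 | 0.79 | 1.00, 1.00 |

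The pre-dose level is 5% to 22% of the 1.5 h level, so in this model the observed maximum is always the 1.5 h sample. After a single dose the lower end is 0.72 instead of 0.75. Nothing comparable can be computed for MET1 or the ratio, because the documents give no MET1 kinetics.

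**The case against.** The case for leaving this alone has real content.

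- **The stakes are low.** The SAP 19.3 outputs are exploratory box and scatter plots with no decision rule. SAP 9 presents Parts A and B separately, so dense and sparse C1D8 values are not mixed in one output. This stands.
- **The concentrations are already reported.** SAP 19.1 lists individual sampling times and summarises concentrations by cycle, day and scheduled time. That also stands, and it reduces the issue to parameters whose names claim more than the data give. It does not correct those names.
- **The error may hardly weaken the plots.** If the ratio were uniform on 0.75 to 1.00, its CV would be (0.25/√12)/0.875 = 0.072/0.875 = 8.2%. With an assumed between-patient CV of 30% (Protocol 5.3 says only that variability was high), reliability is 0.09/(0.09 + 0.0068) = 0.93; with 60% it is 0.36/(0.36 + 0.0068) = 0.98. Slopes would shrink by about 2% to 7%. On those assumptions, this stands.
- **Two post-dose samples are not rich either.** With 1.5 and 4 h samples, tmax is close to a choice between two times. True, but the observed maximum is then 0.89 to 1.00 of the true one over the same range, and this is the line the SAP already draws for Part B AUC(0-4h).

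A reader might infer that the SAP abandoned the protocol's population-PK route. The documents do not support that. Protocol 8.1.2 and 11.4.1.3 already made post-hoc Cmax conditional and placed population PK in a separate plan and report. The synopsis also foresees a separate pooled exposure-response analysis. SAP 19.2 is softer about population PK than Protocol 11.4.1.3, but for post-hoc Cmax the change is small.

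**Conclusion.** The point holds as a specification and labelling error in SAP 19.2. On four of seven Part B days and one of seven Part A days, the listed Cmax and MR_Cmax are a concentration and a ratio at one nominal time, and tmax carries no information. This follows from the sampling tables alone and needs no assumption about kinetics beyond the pre-dose level being the lower of the two.

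The size of the Cmax shortfall cannot be fixed from the documents. The C1D8 range of 0.75 to 1.00 rests on an assumed tmax of 0.5 to 4 h, a one-compartment model and the stated half-life; if tmax is 1 to 2 h, the ratio is 0.97 to 1.00.

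Two stronger readings are tempting. One is that C1D8 Cmax is the exposure measure of the response and safety analyses. It is not: C1D1 Cmax, with two post-dose samples in Part B, comes first in each set, C1D8 Ctrough is also used for response, and tmax is not used in SAP 19.3. The other is that the single-sample Cmax is known to be badly biased or to hide a relation. The documents do not show this, and for QTcF at 0.5 to 2 h the 1.5 h level is roughly time-matched.

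**What to change.** **SAP 19.2.** Restrict Cmax, tmax and MR_Cmax to C1D1, C1D22 and C3D1 in Part B, and to all listed days except C6D1 in Part A. Report the remaining days as the observed 1.5 h or end-of-infusion concentration and MET1-to-parent ratio, with actual time after the Debio 1143 dose and no tmax.

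**SAP 19.3, Part B, response, tumour change and laboratory grades.** Label the C1D8 metric C(1.5h), or use C1D22 Cmax or a population-PK Cmax for D8. C1D22 has 0, 1.5 and 4 h samples in both parts and, like C1D8, falls on the eighth consecutive dose (22 - 15 + 1 = 8). Keep C1D8 Ctrough.

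**SAP 19.3, Part B, QTcF.** Keep C1D8 C(1.5h) and its ratio against C1D8 QTcF at 0.5 to 2 h. If C1D22 Cmax or MR_Cmax is used, pair it with C1D22 QTcF, which Protocol 8.2.2.4 schedules at the same three time points as on D8. Exchanging the exposure alone would set D22 exposure against D8 ECGs. Any C1D8 plot kept against QTcF at 4 to 6 h needs the C(1.5h) label.

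**Cost.** Edits to one SAP table and to some plot specifications; no new samples. Patients who leave between D8 and D22 are lost from any D22 plot; relabelling C1D8 or using the population-PK value avoids that.

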Efficacy of nivolumab monotherapy was assessed in a recent meta-analysis that included 27 worldwide clinical trials (n=5,551). The pooled objective response rate (ORR), the 6-month PFS and the 1-year OS rates were 26% (95% confidence interval (CI) 21–31), 40% (95% CI 34–46) and 52% (95% CI: 43–62), respectively.(14) In Europe, nivolumab (OPDIVO®) as monotherapy or in combination with ipilimumab is currently indicated for the treatment of advanced melanoma, NSCLC, RCC, classical Hodgkin's lymphoma, SCCHN and urothelial carcinoma. Due to antibody-specific kinetics, a flat dose was derived from the 3 mg/kg q2w dose by multiplying for an average 80 kg weight, thus based on the current prescribing information, a nivolumab infusion at either 240 mg (flat dose) q2w or 480 mg every four weeks (q4w) (starting from Cycle 3) was identified as the recommended phase II dose (RP2D). The two treatment schedules are currently being used in daily oncology practice given the extended terminal half-life of IgG4 antibodies such as nivolumab and the relative lack of potential interactions.(12) It is anticipated that switching the nivolumab schedule as of Cycle 3, from D1, 15 q4w to D1 q4w with the higher dose, if the treating investigator considers this appropriate, is not expected to raise any concerns in regards to efficacy or safety, while simplifying treatment administration and hospital visits and contributing to alleviate patient's time constraints and treatment burden to a significant extent.

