Nivolumab will be administered at 240 mg (flat dose) over at least 30 minutes as an IV infusion on Days 1 and 15 of a 28-day cycle. From Cycle 3, patients may be switched to nivolumab at a dose of 480 mg IV over at least 60 minutes on Day 1 q4w, exclusively upon Investigator request with the Sponsor agreement.

The maximum explored Debio 1143 dose will be 200 mg/d. Neither Debio 1143 dose escalation beyond this threshold nor any nivolumab dose increases are foreseen in this study. In individual cases of severe

toxicity, the Debio 1143 dose may be reduced by a maximum of two decrements of 50 mg/d or up to a minimum dose of 100 mg/d.

According to the 3+3 dose-optimization design, if none of the three patients at the starting dose cohort experiences a DLT, three more patients will be treated at the next dose level. However, if one of the first 3 patients experiences a DLT during Cycle 1, 3 more patients will be treated at the same dose level. If  $\leq 1$  out of 6 evaluable patients experience a DLT during the first cycle, at the starting dose level, dose escalation will then proceed to the second dose level. If  $\geq 2$  DLTs are observed during the first cycle among the 3 or 6 evaluable patients treated with the initial dose level, recruitment will then be stopped temporarily or definitively until the reasons for this finding have been clarified. If the dose is increased to the second dose level, 3 to 6 evaluable patients will be included and the 3+3 design rules will be applied again. If  $\leq 1$  out of 6 evaluable patients experience a DLT during the first cycle at the second dose level, this dose will be considered the optimal dose level. If  $\geq 2$  out of 3 or 6 evaluable patients experience a DLT during the first cycle at the second dose level, the initial dose level will then be declared the optimal dose, given that  $< 33\%$  of evaluable patients have experienced a DLT during the first cycle and there are at least 6 evaluable patients treated at this dose level. Patients within a cohort may all start treatment simultaneously.

At least 6 evaluable patients should be treated at the RP2D before Part B of the study may start. Once the RP2D is defined, any patient still receiving treatment can be switched to the RP2D, if deemed appropriate by the Investigator and agreed by the sponsor.

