#### **7.6.2.2. Peri- and post-infusion procedures**

For the infusion, patients must be observed according to standard applicable institutional guidelines, if applicable, or for approximately 90 minutes post-infusion, in an area with resuscitation equipment and emergency agents. At all times during nivolumab treatment, immediate emergency treatment of an infusion-related reaction or a severe hypersensitivity reaction according to institutional standards must be assured.

Infusion of nivolumab will be stopped in case of Grade  $\geq 2$  hypersensitivity, inflammatory response, or infusion-related reactions. Infusions may be resumed after Grade  $\leq 2$  events upon resolution of the events within less than 4 hours and after medical assessment and agreement by a qualified Investigator. Infusion duration will not be shorter than 120 minutes after resumption in all subsequent infusions.

Treatment will be withdrawn definitively after the occurrence of any Grade  $\geq 3$  infusion-related reactions, hypersensitivity or cytokine-release syndrome. Appropriate standard measures must be in place for the medical management of the patients under these circumstances.

Recommendations on how to manage infusion-related reactions and severe hypersensitivity reactions according to the NCI are outlined in section 7.6.2.3.

When a reaction does not resolve completely after 4 hours despite appropriate medical management, the ongoing infusion will not be resumed. Upon Investigator judgement and agreement, next scheduled infusions should be performed at a slower infusion rate (i.e., 120-180 minutes) and pre-medications with standard anti-H1, non-steroidal anti-inflammatory drugs (NSAIDs) and/or low dose steroids might be considered as per standard institutional guidelines.

See section 7.6.2.4 for details on the management of immune-related AEs and sections 5.4 and 7.6.2.3 for other (not immune-related) adverse drug reactions (ADRs) potentially requiring nivolumab discontinuation or temporarily withhold.

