4.3. CHANGES TO ANALYSIS FROM PROTOCOL

Screened Analysis Set

The protocol does not mention a screened analysis set but it has been included in this SAP for the purposes of subject disposition analyses.

Analysis of primary endpoint (ORR)

The protocol mentions reporting ORR at final analysis in terms of relative and absolute frequencies along with a 95% confidence interval. As this is a Bayesian analysis, we need to provide an estimate of the ORR based on the posterior beta distribution along with a 95% credibility interval. This has been described in section 17.1.3.

Pharmacokinetics

Graphical presentation of concentration-time profiles is simplified to depict geometric mean concentrations \pm geometric standard deviations and individual profiles on log₁₀/linear scales.

For the non-compartmental PK analysis, in addition to the analysis for plasma Debio 1143 and Debio 1143-MET1 described in the protocol, PK parameters will also be calculated for serum nivolumab.

Additional descriptive statistics, in addition to the ones specified in the protocol, are included for concentration and PK parameter summaries for consistency with data presentation in previous study. For the list of all descriptive statistics, refer to section 7.6.

Efficacy Analysis Set

As per protocol, treatment failure is defined as any of the following: death, unacceptable toxicity, clinical deterioration and/or symptoms worsening. Treatment failure definition is updated and defined as any: death, unacceptable toxicity, clinical deterioration and/or symptoms worsening, *except those linked to COVID-19*.

The following category is not described in the protocol:

Category 7: Patients whose treatment had to be delayed or interrupted for reasons related to COVID-19 pandemic only and did not receive at least 25% of the planned Debio1143 dose or skipped one nivolumab infusion during cycle 1. Exposure during the first 3 treatment cycles will also be considered as part of the assessment of patients who fall into this category. Planned analysis

Due to the futility of the part B cohorts, no pooling of part A and Part B will be performed.

Document: T:\sas\Debiopharm\Debio_1143\CZA60507\Biostatistics\Documentation\SAP\SAP Text\V5

Author: XXXXXXXXXX Version Number: 5.0
Version Date: 19APR2022

Template No.: CS_TP_BS016 Revision 5
Effective Date: 01Apr2018

Reference: CS_WI_BS005

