Copyright © 2009, 2010, 2012, 2016, 2018 IQVIA. All rights reserved. The contents of this document are confidential and proprietary to IQVIA Holdings Inc. and its subsidiaries. Unauthorized use, disclosure or reproduction is strictly prohibited.

Nivolumab:		Part A	Part B
C_{trough} (ng/mL)	Minimal concentration in serum before next dose obtained directly from the observed concentrations versus time	Cycle 1 day 15 Cycle 3 day 1 and day 15 (only those with 240 mg dose) Cycle 6 day 1	Cycle 1 day 15 Cycle 3 day 1 and day 15 (only those with 240 mg dose) Cycle 6 day 1
AUC_{tau} (ng·h/mL)	Area under the concentration-time curve in plasma from zero (pre-dose) to end of the dosing interval of 15 days	Cycle 1 day 1 (from day 1 pre-dose to pre-dose day 15) Cycle 3 day 1 (from day 1 pre-dose to day 15 (only those with 240 mg dose)	Cycle 1 day 1 (from day 1 pre-dose to pre-dose day 15)
AUC_{inf} (ng·h/mL)	Area under the concentration-time curve in plasma from time of dosing extrapolated to infinity	Cycle 1 day 1 and day 15	
C_{ss} (ng/mL)	Concentration at steady-state, concentration observed at the end of nivolumab infusion	Cycle 1 day 1 and day 15 Cycle 3 day 1 and day 15 (only those with 240 mg dose)	Cycle 1 day 1 and day 15 Cycle 3 day 1 and day 15 (only those with 240 mg dose)
CL (L/h)	Clearance calculated as Rate of nivolumab infusion/ C_{ss}	Cycle 1 day 1 and day 15 Cycle 3 day 1 and day 15 (only those with 240 mg dose)	Cycle 1 day 1 and day 15 Cycle 3 day 1 and day 15 (only those with 240 mg dose)

*Debio 1143 molecular weight: 561.71 g/mol; Debio 1143-MET1 molecular weight: 476.61 g/mol

The following PK parameters for Nivolumab will be listed only as supporting information for AUC_{inf} , but will not be summarized:

λ_z Apparent terminal rate constant (1/h), determined by linear regression of the terminal points of the log-linear concentration-time curve. Visual assessment will be used to identify the terminal linear phase of the concentration-time profile. A minimum of 3 data points will be used for determination.

Document: T:\sas\Debiopharm\Debio_1143\CZA60507\Biostatistics\Documentation\SAP\SAP Text\V5

Author: [REDACTED] Version Number: 5.0
Version Date: 19APR2022

Template No.: CS_TP_BS016 Revision 5
Effective Date: 01Apr2018

Reference: CS_WI_BS005

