Copyright © 2009, 2010, 2012, 2016, 2018 IQVIA. All rights reserved. The contents of this document are confidential and proprietary to IQVIA Holdings Inc. and its subsidiaries. Unauthorized use, disclosure or reproduction is strictly prohibited.

$t_{1/2}$, Interval	The time interval (h) of the log-linear regression to determine λ_z
$t_{1/2}$, N	Number of data points included in the log-linear regression analysis to determine λ_z .
Rsq	Goodness of fit statistic for calculation of λ_z (Regression coefficient).
%AUC _{ex}	Percentage of AUC _(0-inf) obtained by extrapolation, calculated as $[(C_{last}/\lambda_z)/AUC_{(0-inf)} \times 100]$.

The AUCs for Debio 1143, Debio 1143-MET1, and Nivolumab will be calculated using linear up/log down trapezoidal summation.

For Nivolumab AUC_{inf}, if either or both of the following criteria are not met, the corresponding AUC_{inf} value will be listed only but excluded from the summary:

- Rsq (in the calculation of λ_z) > 0.85
- %AUC_{ex} < 15.0%

For each analyte, individual PK parameters will be listed and summarized using descriptive statistics (described in Section 7.6) by cycle and study day. In Part A, the summaries will be presented for each dose level and overall. In Part B, the summaries will be presented for each cohort and overall. In addition, the summaries for nivolumab concentrations will be stratified by Nivolumab regimen (240 mg or 480 mg) as applicable.

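### Two SAP derivations give wrong tabulated values: nivolumab CL divides the infusion rate by an end-of-infusion peak, and a fully adherent 150 mg patient shows 75% Debio 1143 compliance in Cycle 1

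*SAP*

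**What the plan says.** **Nivolumab clearance.** The nivolumab table in SAP 19.2 defines C_ss as "Concentration at steady-state, concentration observed at the end of nivolumab infusion". It then defines CL, in L/h, as "Clearance calculated as Rate of nivolumab infusion" over that C_ss. Both rows apply to C1D1, C1D15, C3D1 and C3D15 in both parts, with a restriction to 240 mg patients in Cycle 3. Parameters are summarised by cycle and day, and CL is not among those that are only listed. Protocol 5.1.1 gives nivolumab 240 mg "over at least 30 minutes as an IV infusion on Days 1 and 15" of each 28-day cycle. Protocol 7.6.2.2 foresees a "slower infusion rate (i.e., 120-180 minutes") after some reactions. Protocol 2.1 justifies the schedules "given the extended terminal half-life of IgG4 antibodies such as nivolumab". The non-compartmental nivolumab analysis is a SAP addition: SAP 4.3 states that "PK parameters will also be calculated for serum nivolumab".

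**Debio 1143 compliance.** SAP 16.1 defines compliance as actual over planned cumulative dose, times 100. Planned dose is the number of cycles started times 4000 mg (20 doses of 200 mg), with no term for the assigned dose. Under SAP 15.1 the numerator is the milligrams actually taken. Part A starts at 150 mg/d, and Protocol 5.3 states a cumulative 3000 mg per cycle for that dose. SAP 16 reports compliance for Cycle 1 and for the full treatment period in the safety set; SAP 9 presents Part A by dose level and overall.

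**The concern.** Rate divided by concentration gives clearance only when a constant infusion has run long enough for input to equal elimination. A half-hour infusion of an antibody with a long half-life is nowhere near that point, and C1D1 follows the first dose. Steady state of the two-weekly schedule does not rescue the formula, because the matching input rate would then be dose over dosing interval, not the rate while the infusion is running. Patients with longer infusions, and all patients at later doses, would appear to clear nivolumab more slowly when nothing had changed. Nivolumab PK in combination is a secondary objective of both parts.

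For compliance, a denominator fixed at the 200 mg level mixes assigned dose with adherence. The Part A table would show 75% beside 100% for equally adherent patients, and the overall Part A row would be pulled down. Treatment compliance is named in the Part A primary objective.

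**Working it through.** **Compliance (exact from the documents)**

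- SAP planned dose per cycle: 20 × 200 = 4000 mg, reproduced.
- Protocol 5.3 at 150 mg/d: 20 × 150 = 3000 mg, reproduced.
- 150 mg patient, all 20 Cycle 1 doses: 3000/4000 = 75%.
- 200 mg patient who missed 5 of 20 doses: 15 × 200/4000 = 75%, the same figure.
- Fully adherent patient with 2 of 6 cycles at 150 mg, then 200 mg: (2 × 3000 + 4 × 4000)/(6 × 4000) = 22000/24000 = 91.7%.
- The same with 2 of 13 cycles at 150 mg: (2 × 3000 + 11 × 4000)/(13 × 4000) = 50000/52000 = 96.2%.
- With the assigned-dose denominator, each fully adherent patient gets 100%.
- The nivolumab denominator of 480 mg is right for both schedules (2 × 240 or 1 × 480).

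**Clearance, without assuming a half-life**

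240 mg over 0.5 h is 480 mg/h; over 2 h it is 120 mg/h. At the same end-of-infusion concentration the SAP formula returns values that differ 4-fold.

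**Clearance, size of the error**

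Assumptions: one compartment, doses every 14 days, half-life 7 to 30 days. With rate R, infusion time T and k = ln 2/half-life, the end-of-infusion concentration at dose n is

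C_end = (R/CL)(1 − e^(−kT)) × S_n, where S_n = Σ e^(−14kj) for j = 0 to n − 1.

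So reported CL/true CL = 1/[(1 − e^(−kT)) × S_n]; volume cancels. C1D1, C1D15, C3D1 and C3D15 are doses 1, 2, 5 and 6. Example: half-life 14 days, T = 0.5 h, dose 1 gives 1 − e^(−kT) = 0.00103 and a ratio of 970.

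| T | Half-life | C1D1 | C1D15 | C3D1 | C3D15 |
|---|---|---|---|---|---|
| 0.5 h | 7 d | 485 | 388 | 364 | 364 |
| 0.5 h | 14 d | 970 | 647 | 501 | 493 |
| 0.5 h | 30 d | 2,078 | 1,206 | 716 | 671 |
| 1 h | 7 d | 243 | 194 | 182 | 182 |
| 1 h | 30 d | 1,039 | 603 | 358 | 335 |

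For infusions of 2 to 3 h the ratio runs from 61 (3 h, 7 d, dose 6) to 520 (2 h, 30 d, dose 1). With true clearance constant, reported CL falls between C1D1 and C3D1 by 485/364 = 1.33-fold (7 d) to 2,078/716 = 2.90-fold (30 d).

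**Can dose/AUC replace it?**

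- Dose/AUC_inf at C1D1: the share extrapolated beyond day 14 is 2^(−14/half-life), that is 25% at 7 d and 50% at 14 d. The SAP criterion of under 15% needs a half-life of at most 14 × ln 2/(−ln 0.15) = 5.1 days.
- AUC_inf at C1D15 includes carry-over from dose 1: 0.25/1.25 = 20% at 7 d, 0.5/1.5 = 33% at 14 d.
- Dose/AUC_tau at C3D1 (Part A, 240 mg patients) overstates CL by 1/(1 − e^(−70k)): 1.00 at 7 d, 1.03 at 14 d, 1.25 at 30 d.

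**The case against.** The formulas cannot be defended, but their consequences can be argued down.

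- **Compliance.** SAP 15 also tabulates the number of Debio 1143 administrations, the cumulative dose and the interruptions, for Cycle 1 and overall, so equally adherent patients at both levels show 20 administrations. The named secondary endpoint is the incidence of discontinuations and modifications, not this percentage. Both points are right. They let a careful reader detect the error; they do not make 75% correct.
- **Clearance is peripheral.** The nivolumab endpoint is concentration profiles and, if appropriate, population PK parameters. The exploratory correlations in SAP 19.3 use no nivolumab CL. This also stands, and it confines the damage to the CL rows. The population model does not displace them: "If deemed appropriate, a population PK approach may be used and will be reported separately".
- **Magnitude.** The fold errors rest on an assumed half-life and a simple model. The PK sampling tables place the infusion start at 0.5 h and its end at 1.5 h, which points to a nominal 1 h infusion and a range of 182 to 1,039 rather than up to 2,078. This is a fair limit on the size. The definitional error and the 4-fold dependence on infusion time need no such assumption.
- **Remedy.** Dose/AUC_inf would fail the SAP's own criterion for every half-life in the assumed range, while AUC_tau at C3D1 is already planned. This stands and is reflected in the fix.

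**Conclusion.** Both derivations are wrong as written and should be corrected. The compliance error is exact: 75% instead of 100% in Cycle 1, and in any cycle taken wholly at 150 mg, with smaller deficits over the full period for patients who later move to 200 mg/d. If the RP2D is 200 mg/d, it concerns dose level 1 and the overall Part A row only. That level has 3 to 6 DLT-evaluable patients, but compliance uses the safety set, so replaced patients may add to the count.

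The tabulated nivolumab CL is not a clearance. That conclusion is certain; its size, roughly two to three orders of magnitude for infusions of 0.5 to 1 h, depends on the assumed one-compartment model and half-life of 7 to 30 days.

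The harm is limited to descriptive tables. DLT evaluability counts missed doses (SAP 6.2), and dose decisions use DLTs and raw-data patient profiles (SAP 5.1), so nothing in the documents shows an effect on RP2D selection. The ORR analysis and futility boundaries do not use either quantity.

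**What to change.** **SAP 19.2.** Delete CL as rate over C_ss, and relabel the C_ss row C_eoi, concentration at end of infusion. Report nivolumab CL from the population PK model if that is run. Otherwise use dose/AUC_inf for C1D1 in Part A only, where the SAP's Rsq and %AUC_ex criteria are met; failing them, the AUC_inf "value will be listed only but excluded from the summary", and CL should be omitted too. Do not use C1D15, because it carries over dose 1. If a non-compartmental figure is still wanted, dose/AUC_tau at C3D1 for Part A patients on 240 mg is a further option, labelled as approximate because it assumes accumulation is nearly complete.

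**SAP 16.1.** Set planned Debio 1143 per cycle to 20 × the patient's assigned dose level (3000 mg at 150 mg/d, 4000 mg at 200 mg/d), changing only from the cycle in which the patient moves to the RP2D. State how a mid-cycle move is counted, since Protocol 5.3 does not tie the move to Day 1.

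**Cost.** Two formulas and some reprogramming; no new data. CL from AUC_inf will be missing for most or all patients, because the criterion needs a half-life of about 5.1 days or less and AUC_inf is not planned in Part B.
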